Title:

A Retrospective Multicenter Study Evaluating ATLANTIS™ Abutments on Implants from Four Manufacturers

Identifier: NCT02496091

Document date: 06-Oct-2014

A Retrospective Multicenter Study Evaluating ATLANTIS™ Abutments on Implants from Four Manufacturers.

Sponsor: Dentsply Sirona Implants, [name]

Background and overall aim

The ATLANTIS abutment is a CAD/CAM solution for patient-specific cement and screw retained implant restorations. The abutments are comprised of a unique combination of four key features, summarized under the term ATLANTIS BioDesign Matrix. Together the key features facilitate the soft tissue management for optimal functional and esthetic results. Using the ATLANTIS VAD (Virtual Abutment Design) software, the abutments are individually designed based on the desired final tooth shape for an esthetic result. Moreover, the software makes it possible to locate the margin in an optimal position, i.e. more coronally, in order to avoid cement-related complications. ATLANTIS abutments are available for all major implant systems.

These abutments were originally developed by a company that was founded 1996 (Atlantis Components, Inc.) and acquired by Astra Tech AB (now integrated in Dentsply Sirona Implants) in 2007.

ATLANTIS abutments are available for implant-abutment interfaces from many different implant manufacturers, while there are implant manufacturers proposing that only their own patient-specific abutments perform well on their implants. The rationale from their side is that other companies do not have access to in house engineering specifications and can therefore not optimally recreate the implant-abutment connection interface. However, the ATLANTIS abutment connection interfaces and abutment screws are specifically engineered and tested for each implant interface for optimal fit and stability, this in order to ensure good clinical results.

The rationale for this retrospective study is to provide scientific data on the clinical performance of titanium and gold-shaded titanium ATLANTIS abutments when connected to implants from four of the major implant manufacturers, whereof one being the ASTRA TECH Implant System (Dentsply Sirona Implants).

Study objectives

Primary objective

The primary objective is to evaluate implant and abutment success.

Success is defined as study implant and abutment still in situ at time of the prospective study visits and no Adverse Device Effects related to the study implant, abutment or adjacent peri-implant tissues are reported during the study. Study start date is when the ATLANTIS abutment(s) was finally delivered / installed and included as part of the permanent prosthetic restoration, and the study ends when the subject leaves the prospective study visit.

Secondary objectives

The secondary objectives of the study are to evaluate:

- Implant and abutment survival
- Soft tissue response, by assessment of Papillae, Plaque, Probing Pocket Depth (PPD) and Bleeding on Probing (BoP)
- Bone tissue response, by measuring of marginal bone levels (MBL).
- Patient Reported Outcomes, by subject rating on chewing function, esthetics and satisfaction.
- Safety, by recording of adverse device effects (ADEs)

Study design

This study is designed as a retrospective and multi-center study. The study population is US individuals previously restored with titanium and gold-shaded titanium ATLANTIS abutments on implants from four manufacturers: BIOMET 3i; Straumann; Nobel Biocare and Dentsply Sirona Implants (only ASTRA TECH Implant System). One hundred eighty individuals will be enrolled, 45 per implant manufacturer is planned. The study includes retrospective data collection from the medical records and data collection from one prospective study visit with a clinical examination.

The active study phase, at the study sites, is estimated to 6 months and includes: contacting, recalling and performing one study visit when the ICF will be signed and the clinical examination performed.

The study start date is when the ATLANTIS abutment(s) was finally delivered / installed and included as part of the permanent prosthetic restoration, and the study ends when the subject leaves the prospective study visit.

Success is chosen as primary objective to show that the ATLANTIS abutment has performed well during the study. This will be the case when the implant and abutment are in situ during study, and no ADEs related to implant, abutment or adjacent peri-implant tissues were reported during study. Thus, the study position is free of complications that could have been caused by the abutment. ADEs related to the prosthesis will only affect success when the investigator has actively judged that the event was caused by the abutment.

Study population

The study population is individuals who received ATLANTIS abutments, between 2010 and 2013, connected to implants from BIOMET 3i, Straumann, Nobel Biocare or Dentsply Sirona Implants (only ASTRA TECH Implant System) replacing one or more teeth, in any position in the mouth, as part of a permanent prosthetic restoration. The partially dentate individuals have received either single-unit crowns or fixed partial or full dentures. The abutments need to be titanium or gold-shaded titanium.

Inclusion criteria

For inclusion in the study subjects must fulfill all the following criteria:

- 1. Having received one or more ATLANTIS abutments included in one or more permanent prosthetic restoration(s)
 - o during 2010, 2011, 2012 or 2013,
 - o made of titanium or gold-shaded titanium (previously market as GoldHue),
 - o connected to implants from: BIOMET 3i; Straumann; Nobel Biocare or Dentsply Sirona Implants (only ASTRA TECH Implant System), irrespective of implantabutment interface.
- 2. Being at least 18 years at day of enrollment.
- 3. Having signed and dated the informed consent form.

2(3) 06-Oct-2014

Exclusion criteria

Any of the following is regarded as a criterion for exclusion from the study:

- 1. Unable to come for study visit.
- 2. Not willing to participate in the study or not able to understand the content of the study.
- 3. Involvement in the planning and conduct of the study (applies to both DENTSPLY Implants staff and staff at the study site).
- 4. Simultaneous participation in another clinical study that may interfere with the present study.

Study products

The investigational product (ATLANTIS abutment) in this study is already included in a restoration in the subject at enrollment, thus this study does not involve the installation of any investigational products.

Statistical methods

If nothing else is stated, descriptive statistics will be given for each variable in the study. This means number of subjects or study positions (n), mean, median, standard deviation (SD), minimum (min) and maximum (max) values will be presented for continuous data and frequencies and percentages for categorical data.

The primary objective is to calculate the proportion of successful study positions. Each study position will be categorized as success (No/Yes). The proportion of successful study positions will be calculated by dividing the number of study positions with success=Yes, by the total number of study positions. This proportion will be presented together with a 95% confidence interval (using the exact Binomial approach) and an average follow-up time. Success will be calculated on a study position level although the sample size calculation provides the number of subjects needed; this approach is chosen since we do not in advance know the number of study positions per subject. Consequently, we assume that study positions within one subject are independent of each other if more than one.

Study timetable

Estimated date of first subject enrolled: January 2015 Estimated date of last subject completed: July 2015

3(3) 06-Oct-2014

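### The only planned success estimate pools all four implant manufacturers; four descriptive estimates beside it would be a cheap improvement, not the repair of an error

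*Combined protocol and SAP*

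**What the plan says.** The primary objective is short: "The primary objective is to evaluate implant and abutment success". Study design gives the purpose: "Success is chosen as primary objective to show that the ATLANTIS abutment has performed well during the study". Statistical methods turns this into a single proportion, found by "dividing the number of study positions with success=Yes, by the total number of study positions", reported with an exact binomial 95% interval and one average follow-up time. The unit is the study position. The number of positions per subject is not known in advance, and positions in the same subject are assumed independent.

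The general rule at the start of Statistical methods provides descriptive statistics for every variable but names no grouping.

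The motivation is more specific. Background and overall aim reports that "there are implant manufacturers proposing that only their own patient-specific abutments perform well on their implants", and gives the rationale as data on the "clinical performance of titanium and gold-shaded titanium ATLANTIS abutments when connected to implants from four of the major implant manufacturers", one of the four being the sponsor's own system. Study design adds: "One hundred eighty individuals will be enrolled, 45 per implant manufacturer is planned".

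**The concern.** The background describes a dispute about whether the abutment works on particular manufacturers' implants, and enrolment is balanced over those manufacturers. The only estimate specified adds them together, including the sponsor's own system, to which the argument about access to in-house specifications does not apply.

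Three things are then out of sight. A weak result on one system can be absorbed by good results on the others. The weight of each system depends on how many positions its subjects contribute, although the quota is set in subjects. Follow-up may also differ between systems, and a single average would not reveal it. If the plan is followed exactly, the report could state that the abutment performed well overall but would have no planned basis for a statement about any one manufacturer. A breakdown added after the data are seen would be open to the suspicion of selective reporting.

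**Working it through.** **Inputs.** From Study design: 180 subjects, 45 per manufacturer, four manufacturers. From Statistical methods: 95% exact binomial interval, taken here as two-sided Clopper-Pearson because sidedness is not stated. From Inclusion criteria: abutments received "during 2010, 2011, 2012 or 2013". From Study timetable: visits from January to July 2015. Success rates, positions per subject and within-subject correlation are assumptions, because the documents give none.

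**The plan's own figure.** 4 × 45 = 180, which agrees. The statistical sample size calculation is mentioned, but its inputs are not in the supplied text, so it cannot be reproduced.

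**What pooling can conceal.** One position per subject is assumed. For x successes in n positions, the Clopper-Pearson limits are the 2.5% quantile of Beta(x, n − x + 1) and the 97.5% quantile of Beta(x + 1, n − x).

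| Successes out of 45, by manufacturer | Pooled | Lowest manufacturer |
|---|---|---|
| 43, 43, 43, 42 | 171/180 = 95.0% (90.7 to 97.7) | 42/45 = 93.3% (81.7 to 98.6) |
| 45, 45, 45, 36 | 171/180 = 95.0% (90.7 to 97.7) | 36/45 = 80.0% (65.4 to 90.4) |

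The planned output is identical in both rows.

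**Weight of one system.** With equal numbers of positions it is 45/180 = 25%. If one manufacturer's 45 subjects had three positions each and the other 135 subjects had one, it would be 135/(135 + 135) = 50%.

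**Follow-up.** The shortest possible is 31 December 2013 to 1 January 2015, about 1.0 year. The longest is 1 January 2010 to 31 July 2015, about 5.6 years. Delivery years may or may not differ between manufacturers; the documents do not say.

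**Precision of a breakdown.** 43/45 = 95.6% (84.9 to 99.5), a width of 14.6 points. The same rate pooled, 172/180, gives 91.4 to 98.1, a width of 6.6 points. The ratio is 14.6/6.6, about 2.2.

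**Effect of several positions per subject.** This is the coverage of the nominal 95% exact interval under a beta-binomial model with 45 subjects:

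| True rate | Positions per subject | Correlation | Coverage |
|---|---|---|---|
| 80% | 2 | 0.1 | 95.6% |
| 80% | 2 | 0.2 | 94.6% |
| 80% | 2 | 0.5 | 91.5% |
| 80% | 3 | 0.2 | 91.7% |
| 80% | 3 | 0.5 | 85.3% |
| 95% | 2 | 0.2 | 96.0% |
| 95% | 3 | 0.5 | about 88% |

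Exact limits are conservative under independence, so mild correlation need not take coverage below 95%. Stronger correlation with more positions does.

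**The case against.** The strongest reply is that nothing in the plan is broken. No objective, hypothesis or design statement promises a comparison or a separate estimate by manufacturer, and the pooled proportion answers the objective as written. That stands. A reader might infer from the title, the quota and the background that the primary analysis contradicts the study's purpose; the documents do not support that. A quota can serve balance alone.

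The breakdown may also exist elsewhere. The supplied document is three pages long and mentions a sample size calculation that it does not show, so some planning detail evidently lies outside it. That also stands: the point concerns the supplied text only.

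Third, a breakdown would not settle the dispute. There is no arm with the manufacturers' own abutments, and enrolment is "irrespective of implantabutment interface", so each manufacturer group may mix several connections. Four estimates would inform the question without resolving it, and they would not be interface-level results.

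Fourth, 45 per group is small and the 36/45 case is invented. Both are true. In the first row of the table the pooled interval contains the lowest group's estimate, and the breakdown would add little. In the second it would add a great deal. The reader of the report cannot know which applies unless the breakdown is shown, and wide intervals are acceptable for description.

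**Conclusion.** The point holds as a worthwhile, low-cost addition. In the supplied text the only success estimate is pooled, and it cannot show whether performance holds on each system. The same 95.0% is compatible with a lowest group at 93.3% or at 80.0%, given the assumed rates and one position per subject. That one estimate is absent from the supplied text is certain; whether it is absent from all planning documents is not.

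Two stronger conclusions should not be drawn. Nothing in the documents suggests that any system actually performs worse; the rates above are illustrations. Nor are exact limits always too narrow when subjects contribute several positions. They can be, depending on the correlation and the number of positions: coverage is still about 96% at a true 95% with two positions and a correlation of 0.2, and falls to about 85% to 88% with three positions and 0.5.

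**What to change.** Keep the pooled proportion as the primary result. Add to Statistical methods:

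- For each of the four manufacturers, report the success proportion with a 95% interval, the number of positions and of subjects, and the average follow-up time.
- Assign each position to the manufacturer of its own implant, since a subject may have more than one position.
- Label these estimates as descriptive, not as powered or interface-level comparisons, and do not use the pooled figure to support a statement about any single manufacturer.
- State that exact binomial limits can be too narrow when positions within a subject are positively correlated, depending on the correlation and the number of positions per subject. Use a subject-clustered interval where subjects contribute more than one position.

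The cost is a few sentences and four table columns, with no extra subjects. The manufacturer must be recorded for each position, whereas the quota alone needs it only per subject. The price in precision is an interval of about 15 points at 43/45. If a fuller SAP already holds this table, the sponsor need only confirm it.

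### The primary 95% confidence interval treats positions within a subject as independent without support, and is too narrow if their outcomes are positively correlated

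*Combined protocol and SAP*

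**What the plan says.** Under Statistical methods, the primary result is the number of successful study positions divided by all study positions. On the interval, the plan says: "This proportion will be presented together with a 95% confidence interval (using the exact Binomial approach) and an average follow-up time".

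It recognises that the units do not match: "Success will be calculated on a study position level although the sample size calculation provides the number of subjects needed". The reason follows: "this approach is chosen since we do not in advance know the number of study positions per subject". It then draws the consequence: "Consequently, we assume that study positions within one subject are independent of each other if more than one".

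The inclusion criteria admit subjects with more than one abutment and more than one restoration. The Study population section adds: "The partially dentate individuals have received either single-unit crowns or fixed partial or full dentures". Success is scored for each position and requires, besides implant and abutment being in place, that "no Adverse Device Effects related to the study implant, abutment or adjacent peri-implant tissues are reported during the study". Under Study design, events of the prosthesis count against success only if the investigator has judged that the abutment caused them.

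Other variables are summarised descriptively by default. The document gives no clustered interval, subject-level success result or sensitivity analysis.

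**The concern.** An exact binomial interval on pooled positions is valid only if positions are independent. The plan's reason does not bear on that. Not knowing the cluster sizes at the planning stage explains why the sample size is in subjects and the analysis in positions. It gives no ground for zero correlation, and it does not force the assumption, because a cluster-based interval needs only the counts observed at analysis.

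Positive correlation is plausible. Positions in one mouth share the same host, and adverse effects in the tissue around the implant count as failure. The rule on prosthesis events closes one route by which positions in a bridge could fail together, but leaves the others open.

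At stake is the stated precision of the only interval given for the primary objective. A study meant to show that the abutment performs well will be read from the estimate and its lower limit. Under positive correlation that limit is too high.

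**Working it through.** **Inputs from the documents.** 180 subjects (4 manufacturers x 45 = 180), exact binomial 95% interval, pooled positions, within-subject correlation taken as 0. The sample size cannot be reproduced, because no expected success rate or target width is given.

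**Inputs assumed.** True success 95% (98% as a variant); ICC 0.1, 0.3 and 0.5; positions per subject as follows:

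- mean 1.2: 1/2/3 with probabilities .85/.10/.05
- mean 1.5: 1/2/3/4 with .70/.17/.06/.07
- mean 2: 1/2/3/4/6 with .50/.25/.10/.10/.05

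**Design effect.** With m the positions per subject, DE = 1 + (E[m²]/E[m] − 1) x ICC, and effective n = n/DE.

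- Mean 2: E[m²] = .50 + 1.00 + .90 + 1.60 + 1.80 = 5.8 and 5.8/2 = 2.9. DE = 1.19, 1.57 and 1.95 at ICC 0.1, 0.3 and 0.5, so 360 positions are worth 303, 229 and 185.
- Mean 1.2: E[m²] = .85 + .40 + .45 = 1.70 and 1.70/1.2 = 1.417. DE = 1.04, 1.13 and 1.21.

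**Example intervals** (Clopper-Pearson, with n replaced by effective n):

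| Data | Planned | ICC 0.1 | ICC 0.3 | ICC 0.5 |
|---|---|---|---|---|
| 342/360, mean 2 | 92.2–97.0% | 91.9–97.2% | 91.3–97.4% | 90.8–97.7% |
| 205/216, mean 1.2, lower limit only | 91.1% | 91.0% | 90.8% | 90.6% |

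**Coverage of the planned interval** (beta-binomial simulation; 80,000 replicates, or 20,000 for the equal-size rows):

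| Positions per subject | True success | ICC 0.1 | ICC 0.3 | ICC 0.5 |
|---|---|---|---|---|
| mean 1.2 | 95% | 96.2% | 95.4% | 94.5% |
| mean 1.5 | 95% | 95.5% | 93.3% | 91.3% |
| exactly 2 | 95% | 95.0% | 93.3% | 91.2% |
| mean 2, skewed | 95% | 94.2% | 90.4% | 86.8% |
| exactly 3 | 95% | 92.6% | 88.2% | 83.6% |
| mean 2, skewed | 98% | 95.1% | 91.9% | 88.0% |

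The exact method is conservative under independence (96.2% with exactly 2 positions and ICC 0), which absorbs a small design effect.

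**Does a clustered interval repair it?** Take Clopper-Pearson on n/D, with D estimated from the data as set out in the fix. Coverage at 95% success is 96.6/96.4/96.2% at mean 1.2, 96.3/95.8/95.5% at mean 1.5 and 96.0/95.5/95.1% at mean 2. At 98% success and mean 2 it is 96.4/95.4/93.8%.

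The repair is weaker for the lower limit when failures are few. At 98% success and mean 2, the chance that the lower limit lies above the truth (nominal 2.5%) falls only from 3.5% to 3.3% at ICC 0.3 and from 5.5% to 5.0% at ICC 0.5. Using the bound D = Σm²/Σm instead, this error was at most 1.3% in every case run, including ICC 1.

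**No failures at all.** With 360 of 360 successes, D = 1 gives a lower limit of 0.025^(1/360) = 99.0%. The bound has effective n = 360/2.9 = 124 and gives 97.1%. Counting 180 subjects gives 98.0%.

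**The case against.** The strongest reply is that the assumption is declared openly, the analysis is descriptive, and no test or threshold hangs on the interval. That stands and limits the weight of the point, but disclosing an assumption does not justify it.

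Both drivers of the effect are assumed, and the shared-host argument is general reasoning, not evidence from this study. That also stands, which is why the claim is conditional.

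The mean number of positions does not settle the size by itself. At ICC 0.3, coverage is 93.3% with exactly two positions each but 90.4% with a skewed mean of two. This is right, and the conclusion has to be qualified by how unequal the counts are. Since single crowns and full dentures are both eligible, unequal counts are likely.

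The text refers to a sample size calculation that it does not show, so further analysis detail may exist elsewhere. That would not remove the independence assumption stated here.

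Finally, the remedy could be called elaborate for one proportion, and its main interval gains little when success is very high. This stands in part: a simpler clustered method would serve, and the weakness with few failures is the reason for adding a bound and a subject-level result.

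**Conclusion.** The concern holds and should be fixed. The independence assumption is unsupported and unnecessary, and under positive within-subject correlation the planned interval overstates precision.

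Under the assumptions above, the effect is negligible if most subjects have one position or the ICC is about 0.1 or less with few positions each. It is marginal at a mean of 1.5, or exactly two positions, with ICC 0.3. It is material at ICC about 0.3 or more when subjects average two positions with unequal counts, or have three each. In the 342/360 example the lower limit moves from 92.2% to 91.3% at ICC 0.3 and to 90.8% at ICC 0.5.

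Confidence in the size is only medium, since neither positions per subject nor ICC is documented. Correlation within sites, possible in a multicenter study, is not covered by these figures; the number of sites is not given.

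**What to change.** Delete the independence sentence, keep the position-level proportion, and insert text such as:

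> The 95% CI will treat subject as the cluster: Clopper-Pearson on n/D, where n is the number of positions and D is the ratio-estimator variance with subject as cluster divided by p(1−p)/n, not below 1 (D = 1 if there are no failures). The same interval with D = Σm²/Σm, m being positions per subject, will be shown as a conservative bound. The distribution of positions per subject, and subject-level success (all positions successful) with an exact binomial 95% CI, will be reported beside it.

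A subject-level bootstrap or a cluster method on the logit scale would also do. An untransformed robust Wald interval would not: at mean 2 its coverage is 93.0/91.8/91.0% at 95% success and 90.5/88.2/86.0% at 98%.

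The SAP should state three limits:

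- D is poorly estimated when failures are few, and with none the main interval returns to the planned one.
- Subject-level success is a different estimand.
- Correlation within sites is not handled.

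**Cost.** SAP wording, a few lines of code, one count table and one subject-level result; no extra data or patients. At 95% success and mean 2, the main interval is about 2% wider than planned at ICC 0, and 9%, 25% and 40% wider at ICC 0.1, 0.3 and 0.5. At mean 1.2 the figures are 1%, 3%, 6% and 10%. The conservative bound is 21%, 47% and 78% wider at means 1.2, 1.5 and 2, so it belongs as a sensitivity result only.
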